6.4 Primary Outcome

Our primary outcome of interest is the diagnosis of oesophageal cancer during follow up (all

types and subdivided into adenocarcinoma or squamous cell cancer). We will ascertain the diagnoses on the basis of a diagnosis recorded in any of the four linked data sources (1) patients GP record (2) on their linked mortality record (3) hospital record or (4) cancer registry record. We will use the earliest recorded date of oesophageal cancer diagnosis on any of the four data sources as the index date.

6.5 Secondary outcome

Our secondary outcome is the diagnosis of Barrett's Oesophagus.

6.6 Predictor variables

We will examine the following candidate predictor variables based on 12 risk factors already in the QCancer tool¹³ (marked with an asterix) as well as risk factors identified in the literature. The predictor list can be amended by future updates as new knowledge on emerging risk factors becomes available.

6.6.1 Demographic variables

- 1. Age (continuous variable)*.
- 2. Townsend deprivation score*. This is an area-level continuous score based on the patients' postcode³⁰. Originally developed by Townsend³⁰, it includes unemployment (as a percentage of those aged 16 and over who are economically active); non-car ownership (as a percentage of all households); non-home ownership (as a percentage of all households) and household overcrowding. These variables are measured for a given area of approximately 120 households, via the 2011 census, and combined to give a "Townsend score" for that area. A greater Townsend score implies a greater level of deprivation.
- 3. Ethnicity (9 categories)

6.6.2 concurrent medication (at study entry)

- 1. Proton pump inhibitors (which are used to treat reflux symptoms)
- 2. H2 blockers (which are used to treat reflux symptoms)
- 3. NSAIDs (which can worsen reflux symptoms)
- 4. Aspirin (which may lower OAC risk)^{14 16}
- 5. Statins (which may lower OAC risk)^{17 31}
- 6. COX inhibitors (which may lower OAC risk)¹⁷
- 7. Metformin (which may lower OAC risk)¹⁵
- 8. HRT (in female only, may lower OAC risk)¹⁵
- 9. Other diabetic drugs

6.6.3 Lifestyle and family history

- 4. Smoking status non-smoker, ex-smoker, light smoker (1-9/day), moderate (10-19/day) or heavy(20+/day)*.
- 5. Body mass index (continuous variable, z-scores will be used)*.
- 6. Alcohol use -non-drinker; light drinker (<1 unit/day); moderate (3-6 units/day); heavy (6+ units/day)*.
- 7. Family history of bowel or gastric or colorectal cancer.

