4.3 Enhancing the primary care clinical pathway

Currently the clinical pathway for reflux in primary care relies on excluding alarm symptoms (e.g. dysphagia, weight loss) and managing reflux symptoms with acid-suppressant medication. The NICE guidelines recommend endoscopy via the 2 Week Wait pathway if alarm symptoms are present, and routine referral if the symptoms are persistent and occur in the context of other risks factors such as family history (CG27). If a patient is referred to secondary care via the routine pathway the vast majority of patients will be triaged straight to endoscopy. Clinic appointments in secondary care may be led by a dyspepsia nurse or a Gastroenterologist depending on the local policy and resources.

The current, conventional care pathway has a strong focus on triggering endoscopies which results in high costs for the NHS. Additionally, around 70% of these endoscopies are normal with no clinically significant finding (Endoscopy Service Report). The proposed, enhanced care pathway in this project implements a nurse/pharmacist-led clinic for patients with reflux predominant symptoms whereby a Cytosponge procedure is performed in a one-stop visit. This serves as an intermediate step in which the Cytosponge results, together with the high specificity of the test, are used to avoid unnecessary endoscopies.

The CytospongeTM can be readily placed into this pathway (see Fig). We propose that primary care individuals at high risk including those undergoing repeat prescriptions for reflux symptoms are considered for a CytospongeTM test, with more consideration given to their requirement for long term PPI medication as part of this process. The patients could be flagged electronically to a GP and the test performed by the practice nurse. Alternatively, with the expanding role of the community Pharmacist they would be ideally placed to perform this role. Thus, only patients deemed to be at risk for Barrett's oesophagus (or another oesophageal condition, or gastric IM) ascertained by the CytospongeTM test would be referred for endoscopy.

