6.8.4 Variable selection

We will fit models that include all predictor variables initially and retain variables if they have a hazard ratio of < 0.90 or > 1.10 (for binary variables) and are statistically significant at the 0.01 level. For previous diagnoses of other cancers, we will retain variables which were significant at the 0.05 level since some of the cancers are rare. In order to simplify the models, we will focus on variables for the most common conditions and medications and combine similar variables with comparable hazard ratios where possible. If some predictor variables result in very sparse cells (i.e. with not enough participants or events to obtain point estimates and standard errors), we will combine some of these if clinically similar in nature.

For PPI and H2 blockers medication usage, we will determine the association between risk of oesophageal cancer and type of medication (omeprazole etc), dose and duration of exposure (e.g. < 6 months; 6-11 months; 12-23 months; 24-47 months; 48 months or more). We will examine both usage at baseline and also as a time varying exposure during study follow-up.

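### The only family-history candidate predictor does not name oesophageal cancer, the outcome being predicted, so that family history is not tested in this model development

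*Protocol*

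**What the plan says.** Protocol section 6.4 sets the outcome: "Our primary outcome of interest is the diagnosis of oesophageal cancer during follow up", for all types and for the adenocarcinoma and squamous subtypes.

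Section 6.6 introduces the predictors: "We will examine the following candidate predictor variables based on 12 risk factors already in the QCancer tool" (marked by asterisk), "as well as risk factors identified in the literature". The one family-history entry, item 7 of section 6.6.3, is "Family history of bowel or gastric or colorectal cancer". It has no asterisk, so it is a literature-based candidate and not one carried over from the existing tool. No entry under demographics, medication, or co-morbidities and investigations refers to family history.

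Section 6.8.4 says how the list is used: "We will fit models that include all predictor variables initially". Binary variables are then kept if the hazard ratio lies outside 0.90 to 1.10 and the 0.01 significance level is met. Similar or sparse variables may be combined.

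Section 6.6 leaves one door open: "The predictor list can be amended by future updates as new knowledge on emerging risk factors becomes available".

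In the background, section 4.3 describes guideline practice for reflux as "routine referral if the symptoms are persistent and occur in the context of other risks factors such as family history". It does not say which cancer.

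**The concern.** A prediction model for one cancer would ordinarily consider family history of that cancer among its candidates. Here the family-history item names other digestive sites and leaves out the outcome site, and the protocol gives no reason. The protocol's own account of the referral pathway treats family history as something that changes a patient's management.

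Two things follow if the plan is carried out as written. A patient whose only recorded family history is of oesophageal cancer does not meet the definition in item 7 and falls into the reference category. And the analysis cannot show whether that factor predicts the outcome, because it never reaches the retention rule. A reader of the published model could take family history to have been considered when the outcome-specific form of it was not.

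**Working it through.** This is mainly a check of text against text.

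1. **Outcome against predictor.** Section 6.4 names oesophageal cancer. Item 7 of section 6.6.3 names bowel, gastric and colorectal cancer. The outcome site is absent.

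2. **Other entries.** The lists in sections 6.6.1 to 6.6.4 contain no second family-history item. The cancers in section 6.6.4 are the patient's own diagnoses.

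3. **Does the list bind?** Section 6.6 says the listed candidates will be examined, and section 6.8.4 starts from a model with all of them. Amendment is foreseen through future updates for emerging risk factors.

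4. **Does a later step repair it?** Section 6.8.3 imputes ethnicity, Townsend score, body mass index, smoking and alcohol. Family history is not among them. A patient with only an oesophageal family history stays coded as not having item 7.

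5. **The synonym.** Bowel and colorectal name largely the same site, though bowel could be read to include small bowel. Because the terms are joined by *or* in a single item, the overlap adds no parameter and moves no patient between groups.

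**What would a correction cost in sample size?** The inputs, from section 6.8.9, are P = 70 parameters, R² = 0.002013 (men) and 0.0009468 (women), mean follow-up 1.74 years, and event rates 0.00064 and 0.00031. The shrinkage target S is not stated; S = 0.9 is my assumption, and it reproduces the plan's figures.

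Formula: n = P / [(S − 1) × ln(1 − R²/S)]; events = n × 1.74 × event rate.

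| | P | n | Events |
|---|---|---|---|
| Men, as planned | 70 | 312,616 (stated 312,616) | 348.1 (stated 349) |
| Women, as planned | 70 | 665,050 (stated 665,050) | 358.7 (stated 359) |
| Men, one more parameter | 71 | 317,082 | 353.1 |
| Women, one more parameter | 71 | 674,550 | 363.9 |

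The increase is 71/70 − 1 = 1.4% in each sex. The events needed at P = 71 total about 353 + 364 = 717. Section 6.8.9 reports at least 18,000 cases. If cases divide as the practices do, three quarters to derivation, that gives about 0.75 × 18,000 = 13,500 before exclusions. Simply adding oesophageal cancer to the existing composite adds no parameter and changes nothing in the table.

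**The case against.** The strongest reply is that the protocol does not show the omitted factor to matter. It gives no effect size, recording frequency or specific citation for family history of oesophageal cancer; section 4.3 names no site and only reports guideline practice; and the literature behind item 7 cannot be checked from the document. This stands. It limits any claim about lost performance, but it does not explain why the outcome site was left out of a candidate list whose purpose is to let the data decide.

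Code lists may also be kept in a separate document and could be broader than the label. That is possible, but item 7 names its sites explicitly, and a code list that follows it would exclude oesophageal cancer.

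Some stronger readings are tempting, and the document does not support them:

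- *The factor can never be tested.* Section 6.6 allows future amendment. The accurate statement is that it is not tested in this development.
- *Every patient with this family history is misclassified.* Anyone who also has a recorded bowel, gastric or colorectal family history is coded as exposed.
- *The composite is dominated by bowel cancer, so family history will drop out of the model.* The protocol has no figures on the mix of sites or their hazard ratios.
- *A known share of cases is affected.* With an assumed recorded prevalence q of 0.5% to 2% and hazard ratio HR of 1.5 to 3, the share of cases carrying the factor, q × HR / [1 + q × (HR − 1)], runs from 0.75% to 5.8%. Neither input comes from the protocol, and the result is not a loss of discrimination or calibration.
- *The bowel/colorectal repetition is an analysis error.* It is loose wording with no effect on results.

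**Conclusion.** The point holds in a limited form. Item 7 omits the outcome cancer, nothing else in the candidate list covers it, and following the plan leaves that predictor untested in this development, with patients who have only that family history in the reference group. The effect on the model's performance cannot be quantified from the protocol and may be small. This is a minor, low-cost improvement, and it does not call the design or the sample size into question.

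The conclusion rests on two assumptions: that the code list for item 7 follows its wording, and that a recorded family history of oesophageal cancer exists often enough to be worth examining. The second is for the data and the existing retention rule to settle.

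**What to change.** Amend item 7 of section 6.6.3 before model fitting so that oesophageal cancer is among the family-history sites. The preferable form is two candidates: family history of oesophageal or gastric cancer, and family history of colorectal cancer. This keeps an upper-gastrointestinal signal from being averaged with a lower one. The minimal form is to add oesophageal cancer to the existing composite. In either case the retention and combination rules of section 6.8.4 apply unchanged. If the omission is deliberate, one sentence giving the reason would do instead.

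Tidy the overlapping bowel and colorectal terms in the same edit.

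The cost is one extra code list and at most one extra parameter, or none if the planning ceiling of 70 still has room. The term may drop out or have to be combined if recording is sparse.

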6.6.4 Co-morbidities and investigations

- 8. gastric cancer
- 9. Barrett's oesophagus*
- 10. Peptic ulcer disease*
- 11. Gastro-oesophageal reflux disease (including heart burn)
- 12. Type 1 and type 2 diabetes*
- 13. previous blood cancer*
- 14. previous breast cancer*
- 15. previous oral cancer*
- 16. previous pancreatic cancer*
- 17. Current H.Pylori infection (which may lower OAC risk)
- 18. pernicious anaemia
- 19. hiatus hernia
- 20. anaemia (including Haemoglobin values)
- 21. Full blood count
- 22. CT scan abdomen within the previous 5 years
- 23. CT scan pelvis within the previous 5 years
- 24. Barium meal/swallow within the previous 5 years
- 25. Endoscopy within the previous 5 years

All predictor variables will be based on the latest coded information recorded in the GP record prior to entry to the cohort.

6.7 **Descriptive analysis**

We will produce the following descriptive analyses for comparison with the literature and national statistics from the CRUK website.

- crude incidence of oesophageal cancer by age, sex, ethnicity, deprivation and calendar time.
- age standardised incidence of oesophageal cancer overall and by type.
- characteristics of cases diagnosed with oesophageal cancer age at diagnosis, stage, grade, histology, treatment (surgery, radiotherapy, chemotherapy, other).

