6.8.3 Handling of missing data

For all predictor variables, we will use the most recently available value at the time origin. For indicators of co-morbidities and medication use, the absence of information being recorded is assumed to mean absence of the factor in question. There may be missing data in some variables due to never being recorded: ethnicity, Townsend score, body mass index, smoking status and alcohol intake. We will use multiple imputation with chained equations to replace missing values for these variables ³⁶⁻³⁹.

Prior to the imputation, a complete-case analysis will be fitted using a model containing only the continuous covariates within the derivation data to derive the fractional polynomial order and corresponding powers. Then a multiple imputation model using chained equations will be fitted in the derivation data and will include all predictor variables along with age interaction terms, the Nelson–Aalen estimators of the baseline cumulative hazard, and the outcome indicators (namely, oesophageal cancer). Separate imputation models will be fitted for men and women. We will carry out 5 imputations as this has a relatively high efficiency²⁹ and is a pragmatic approach accounting for the size of the datasets and capacity of the available servers and software.

Each analysis model will be fitted in each imputed data set. We will use Rubin's rules to combine the model parameter estimates across the imputed datasets⁴⁰.

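### The predictor labelled current H. pylori infection compares people with a positive GP code against a mix of tested-negative and never-tested people, so its weight does not belong to the variable it names

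*Protocol*

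**What the plan says.** Item 17 in Protocol section 6.6.4 is "Current H.Pylori infection (which may lower OAC risk". The section closes with a rule for every predictor: "All predictor variables will be based on the latest coded information recorded in the GP record prior to entry to the cohort". Items 22 to 25 in the same list (CT, barium studies, endoscopy) carry a five-year look-back. Item 17 has no look-back, and nothing says how a treated infection is handled.

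Section 6.8.3 adds: "For indicators of co-morbidities and medication use, the absence of information being recorded is assumed to mean absence of the factor in question". The variables it recognises as possibly missing, and imputes, are "ethnicity, Townsend score, body mass index, smoking status and alcohol intake". H. pylori is not among them, and no other section exempts it.

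Section 6.8.4 fits all predictors together and will "retain variables if they have a hazard ratio of < 0.90 or > 1.10 (for binary variables) and are statistically significant at the 0.01 level". No direction of effect is required.

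**The concern.** Assuming absence when nothing is recorded is workable for a diagnosed disease that would normally reach the record. It works less well for an infection that is recorded only when someone tests for it. Under the stated rules a person never tested is coded the same as a person tested and found negative, so the reference group is mixed. A positive code with no later coded result also stays current however old it is, and whether or not the infection was treated.

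Two consequences follow. First, the hazard ratio for infection is diluted by infected people in the reference group. Second, if the people tested differ in cancer risk from those not tested, that difference enters the coefficient. Section 4.1 names chronic reflux as a major risk factor, and the exclusions in section 6.2.3 remove only recent alarm symptoms, so people with ordinary reflux or dyspepsia stay in the cohort.

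At stake is the meaning of the weight when the tool leaves the coded record. Section 6.9.4 foresees versions in which users type in their own information, and section 5 foresees adaptation for the general public. Someone stating that they have a current infection is not reporting a positive latest GP code, and someone stating that they do not is not reporting the absence of any code.

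**Working it through.** The protocol gives no figure for this predictor, so there is nothing to reproduce. All inputs below are assumptions, chosen to show the size of the effect:

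- true hazard ratio for infection, 0.6
- infected among the untested, 30%
- positive among the tested, 25%
- share tested before entry, *t* = 5%, 10% or 15%
- *s* = risk in tested relative to untested people of the same infection status, left over after the other predictors in the model are adjusted for
- an accurate test and a rare outcome

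**Composition of the groups.** The group coded uninfected has size (1−t) + 0.75t. At t = 0.10 this is 0.900 + 0.075 = 0.975. Never-tested people make up 0.900/0.975 = 92% of it, and untested infected people 0.30 × 0.900/0.975 = 28%. Over t = 5–15% these shares run 96–88% and 29–26%. The positive code captures 0.25t of 0.25t + 0.30(1−t) infected people: 0.025/0.295 = 8% at t = 0.10, and 4–13% over the range.

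**Coded hazard ratio.** The average relative risk among untested people is 0.7 + 0.3 × 0.6 = 0.88. Then

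coded HR = 0.6s ÷ { [0.88(1−t) + 0.75ts] / [(1−t) + 0.75t] }.

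Example, t = 0.10 and s = 1.5: reference = (0.792 + 0.1125)/0.975 = 0.928; coded HR = 0.9/0.928 = 0.97.

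| s | t = 5% | t = 10% | t = 15% | Hazard-ratio part of the retention rule |
|---|---|---|---|---|
| 1.0 | 0.68 | 0.67 | 0.67 | met, lower risk |
| 1.3 | 0.87 | 0.85 | 0.84 | met, lower risk |
| 1.5 | 1.00 | 0.97 | 0.94 | not met |
| 2.0 | 1.30 | 1.24 | 1.19 | met, higher risk |

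**Turning points at t = 10%.** Setting the coded HR to X gives s = 0.792X/(0.585 − 0.075X). X = 0.90 gives s = 1.38; X = 1.00 gives 1.55; X = 1.10 gives 1.73. With a single infection prevalence in tested and untested people, and wider assumptions (true HR 0.50–0.75, 5–20% tested, prevalence 15–40%), the point where the association reverses lies between s = 1.21 and s = 2.35.

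**With tested people kept separate.** Positive versus negative is 0.6s/s = 0.6 whatever s is, provided testing marks the same extra risk in both tested groups.

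**The case against.** The strongest answer is that this is a prediction tool. Section 6.8.5 uses coefficients as weights in a risk equation, and the protocol does not set out to estimate the causal effect of infection. If code-positive patients really carry 1.2 times the risk of everyone else, 1.2 is the correct weight for that code, and dropping a marker near 1 costs little. This stands. A reader might infer that the model would hold a coefficient of the wrong sign and mis-rank patients within QResearch; the documents do not support that. The remark about lower adenocarcinoma risk gives a reason for considering the predictor and is not a hypothesis under test. The primary outcome in section 6.4 also includes all types, so an all-type coefficient that is not protective would not contradict it.

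Further points also stand:

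- The variable can be derived. A reader might conclude that it cannot, but the coding rule is stated.
- Because the latest code is used, a coded negative retest would replace an earlier positive. The gap is treatment without a coded retest.
- Testing on symptoms is an inference. Without such selection the effect is attenuation only.
- The other candidates include "Gastro-oesophageal reflux disease (including heart burn", "Proton pump inhibitors (which are used to treat reflux symptoms", H2 blockers, peptic ulcer disease and recent endoscopy. Only the residual risk matters, and at 1.0 to 1.3 the coded HR stays below 0.90.

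It can also be said that code lists belong in an analysis plan not shown here. That answers the missing look-back. It does not answer the absence rule, which the protocol fixes itself.

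**Conclusion.** The point holds as a mislabelled predictor with a mixed reference group. As the plan stands, item 17 measures whether the latest GP code is positive, against a group that is mostly never tested and partly infected.

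Under the assumed inputs a true hazard ratio of 0.6 becomes 0.67–0.68 with no residual testing risk, and is lost or reversed only if that residual risk ratio exceeds roughly 1.4 to 1.6. Attenuation is to be expected whenever untested people include infected ones. Loss or reversal is possible, but the protocol offers nothing to say how likely it is.

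Performance inside QResearch may be unaffected, and for that reason internal validation cannot reveal the problem: the validation practices in section 6.2.1 come from the same database and use the same coding rule. The exposure is in user-entered versions and in settings where testing or coding differs. The change is cheap and worth making before the predictor is coded.

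**What to change.** In section 6.8.3, exempt item 17 from the rule that "the absence of information being recorded is assumed to mean absence of the factor in question". In section 6.6.4, replace it with a variable of three levels: no H. pylori test on record, latest test negative, latest test positive. Where numbers permit, hold positives with a later eradication prescription as a fourth level and do not merge them with never-positive patients. State any look-back used to call a result current. Name the variable *recorded H. pylori status* in the model and in every user-entry version, with a response for people who have not been tested.

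The cost is a code list and a data step using test and prescription records expected to be in the GP data, plus one or two more parameters. The positive-versus-negative contrast will have a wider interval because it rests on tested people only.

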6.2.3 Patient exclusions

Exclusions will broadly match those for WP2 which aims to implement the risk algorithm for recalling patients for the Cytosponge and hence the following will be excluded

- Patients with a new onset of alarm symptoms (including haematemesis, unexplained weight loss, dysphagia) in the last 3 months before study entry since these are likely to require urgent referral on the 2-Week Wait pathway for endoscopy.
- Recorded diagnosis of a current or previous oro-pharynx, oesophageal or gastrooesophageal tumour
- Received prior surgical intervention to the oesophagus
- Recorded oesophageal varices, cirrhosis of the liver

Patients with recorded Barrett's oesophagus will be included and the presence of Barrett's oesophagus will be evaluated as a risk factor.

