6.8.2 Development of the models using the derivation data

For all analyses, the time origin is entry to the study cohort and the risk period of interest is from the time origin up to the first date of diagnosis of oesophageal cancer. We will develop and evaluate the risk prediction equations using established methods^{19 32-35} We will use second degree fractional polynomials (i.e. with up to two powers)³¹ to model non-linear relationships for continuous variables (age, body mass index and Townsend score). Models will include interactions between age and predictor variables focussing on predictor variables which apply across the age range where numbers allow.

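### The endoscopy and barium predictors (and, less clearly, CT) run up to the day follow-up starts, so a test that is part of a cancer's own work-up can be scored as a predictor of it

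*Protocol*

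**What the plan says.** Protocol section 6.6.4, items 22 to 25, names four investigation predictors: CT abdomen, CT pelvis, barium meal or swallow, and endoscopy. The wording is the same throughout, for example "Barium meal/swallow within the previous 5 years" and "Endoscopy within the previous 5 years". The window has a far edge of 5 years and no near edge. The section closes with "All predictor variables will be based on the latest coded information recorded in the GP record prior to entry to the cohort", and section 6.8.3 repeats the rule: "For all predictor variables, we will use the most recently available value at the time origin".

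Section 6.8.2 sets the start of follow-up: "the time origin is entry to the study cohort and the risk period of interest is from the time origin". Predictor capture therefore ends, and outcome counting begins, on one date. Section 6.3 makes that date administrative: study start, 25th birthday, or 12 months after registration, whichever is latest.

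Section 6.2.3 gives a partial safeguard. It excludes people with new alarm symptoms "in the last 3 months before study entry since these are likely to require urgent referral on the 2-Week Wait pathway for endoscopy", and people with a tumour already recorded. Section 6.4 dates the outcome at the earliest record in any of four sources. Section 6.8.4 keeps a binary variable if its hazard ratio is below 0.90 or above 1.10 and it is significant at the 0.01 level.

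**The concern.** Because entry is unrelated to any diagnostic episode, it can fall between a test and the diagnosis that the test produces. The tumour exclusion does not catch such a person, since the tumour is recorded after entry. The alarm-symptom exclusion catches them only if an alarm symptom was newly coded in the preceding 3 months. Section 4.3 describes another route to endoscopy: routine referral for persistent symptoms with other risk factors, mostly triaged straight to the procedure.

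The plan already accepts the principle for symptoms, removing people who are on their way to urgent endoscopy. It does not apply it to people who have just had the endoscopy.

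At stake are the coefficient, which would carry part of the diagnostic process into a 10-year risk score, and the 1- and 2-year statistics of section 6.8.6, where the artefact is concentrated. The validation practices use the same definitions, so the planned validation would reproduce the artefact and not reveal it.

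**Working it through.** **The plan's own figures.** The protocol gives no figure for this point. Its sample size (6.8.9) supplies the background numbers and reproduces. With 70 predictors and an assumed shrinkage target of 0.9, n = 70 / [(0.9 − 1) × ln(1 − R²/0.9)].
- Men (R² 0.002013): 312,616, and 312,616 × 1.74 × 0.00064 = 348.1 events (stated: 349).
- Women (R² 0.0009468): 665,049 (stated: 665,050), with 358.7 events (stated: 359).

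**Inputs from the protocol.** At least 18,000 cases (6.8.9), of which three quarters are in the derivation practices (6.2.1): 0.75 × 18,000 = 13,500. Retention limits are 1.10 and the 0.01 level (6.8.4), taken as two-sided, z = 2.576.

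**Assumptions, not in the protocol.**
- Test coded in the 5-year window: endoscopy 5% or 10% of the cohort; barium 1%.
- Share of cases preceded by the test: 90% endoscopy, 25% barium.
- Gap from GP-coded test to first recorded diagnosis: 2 to 8 weeks.
- Alarm-symptom exclusion removes half of the cases that straddle entry.
- Cases split 67:33 by sex: 9,045 men, 4,455 women.
- True hazard ratio of the test is 1, constant hazard, no adjustment for other predictors.

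**Step 1: factor on the hazard ratio over 10 years.** Extra cases among the tested are rate × (weeks/52) × share × 0.5. Expected cases among the tested are rate × prevalence × 10. The rate cancels:

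factor = 1 + 0.5 × share × (weeks/52) / (prevalence × 10)

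| Test, prevalence | 2 weeks | 4 weeks | 8 weeks |
|---|---|---|---|
| Endoscopy, 5% | 1.03 | 1.07 | 1.14 |
| Endoscopy, 10% | 1.02 | 1.03 | 1.07 |
| Barium, 1% | 1.05 | 1.10 | 1.19 |

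Example, endoscopy at 5% and 8 weeks: 0.5 × 0.9 × 0.1538 / 0.5 = 0.138. The 4-week barium value is 1.096, just under 1.10. Endoscopy at 5% passes 1.10 beyond 0.1 × 0.5 × 52 / 0.45 = 5.8 weeks; barium beyond 0.1 × 0.1 × 52 / 0.125 = 4.2 weeks. Without the halving, the ranges are 1.07–1.28 (endoscopy, 5%), 1.03–1.14 (endoscopy, 10%) and 1.10–1.38 (barium). Over the first year only, with halving, endoscopy at 5% gives 1.35 to 2.38.

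**Step 2: adding the significance limit.** For k straddling cases, all tested, HR = (exposed events/p) / (unexposed events/(1 − p)) and z = ln HR / √(1/exposed events + 1/unexposed events). The smallest k meeting both limits is:

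| Prevalence p | Men (9,045) | Women (4,455) |
|---|---|---|
| 1% | 25 (0.28%) | 18 (0.40%) |
| 5% | 57 (0.63%) | 40 (0.90%) |
| 10% | 90 (1.00%) | 58 (1.30%) |

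**Step 3: how many to expect.** Straddling share of cases = gap / mean follow-up × share tested × 0.5.

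| | 4 weeks | 8 weeks |
|---|---|---|
| Endoscopy, mean follow-up 5 years | 0.69% | 1.38% |
| Endoscopy, 7 years | 0.49% | 0.99% |
| Endoscopy, 10 years | 0.35% | 0.69% |
| Barium, 5 years | 0.19% | 0.38% |
| Barium, 7 years | 0.14% | 0.27% |
| Barium, 10 years | 0.10% | 0.19% |

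Set against Step 2, endoscopy at 5% passes in men at 4 weeks with 5 years' mean follow-up, and at 8 weeks with 5, 7 or 10 years. In women it passes at 8 weeks with 5 or 7 years. At 10% it passes only at 8 weeks with 5 years. Barium passes in men only, at 8 weeks with 5 years and at the margin with 7 (z = 2.59). At 1 or 2 weeks nothing passes with mean follow-up of 5 years or more. At the 1.74 years used in section 6.8.9 the shares are several times larger, and endoscopy at 5% passes in both sexes from 2 weeks.

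**The case against.** The best reply is that the plan already narrows the gap. The alarm-symptom exclusion removes many work-ups, and dating the outcome at the earliest of four sources tends to bring the diagnosis close to the test or to make the person ineligible as an existing case. This stands: it is why the factors are halved, and why the point fails at gaps of a week or two with long follow-up. The halving is itself an assumption.

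A second reply is that the items are only candidates on an amendable list, and that lag rules may sit in an analysis plan not shown. The protocol does, however, fix the look-back and the end of capture, twice, so a lag would have to change its text.

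Third, CT is weaker. Nothing makes CT pelvis an evident route to this diagnosis, and CT may follow the recorded cancer. No size is claimed for CT.

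A reader might go further and infer that the score would be raised for people with an earlier clear endoscopy who are not meant to be offered Cytosponge. The protocol does not say so: prior endoscopy is not among the exclusions in 6.2.3. Nor does it show that older tests mark lower risk, since the item covers any endoscopy, whatever the result. If they did, the artefact would find it harder to reach 1.10: at a true hazard ratio of 0.8, men would need 0.48% to 2.97% of cases across prevalences of 1% to 10%, against 0.28% to 1.00% at a true ratio of 1.

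**Conclusion.** The definitional fault is in the text: the predictor window and the outcome window meet with no gap, and the 3-month safeguard covers coded symptoms but not the tests themselves. The direction of the bias is upward, strongest in the early years, and invisible to the planned validation.

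The size is conditional. Under the stated assumptions the 10-year factor is about 1.03–1.14 for endoscopy at 5% prevalence and 1.05–1.19 for barium at 1%. Both parts of the retention rule can be met by the artefact alone in part of the range, more readily for endoscopy in men. It would be too strong to say that these tests will be retained for this reason. Prevalence, share tested, gap, mean follow-up in the cohort and the effect of the exclusion are all assumed, and the calculation is unadjusted. It is a change worth making before the models are fitted, not a threat to the study.

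**What to change.** In section 6.6.4, count items 22 to 25 only when dated more than 3 months and up to 5 years before entry, matching the 3-month window in 6.2.3. Add a sensitivity analysis that drops events in the first 3 months of follow-up and reports the investigation coefficients and early performance measures again.

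Do not exclude everyone recently endoscoped. Section 6.2.3 expressly keeps people with Barrett's oesophagus, and some of them will have had a recent endoscopy.

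The cost is one date filter and one extra analysis. A few recently tested people are coded as untested, but that group is large. On the endoscopy inputs at 5% and 8 weeks, even without the halving, the added cases are 0.9 × 0.1538 / (0.95 × 10) = 1.5% of those expected, so the hazard ratio falls by about that much. Dropping the first 3 months loses 1 − exp(−0.25 / mean follow-up) of events: 4.9% at 5 years, 2.5% at 10 years, and 13.4% at the 1.74 years of section 6.8.9. From about 13,500 derivation cases, any of these leaves far more than the 349 + 359 = 708 events that the plan requires.
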